
C.8.7. Additional Exploratory Analyses. We may also conduct exploratory analyses of associations among other measures collected as part of this study. This may include associations among variables at baseline, potential roles of baseline variables as moderators or mediators of treatment effects, or association of baseline variables with intervention uptake and outcomes.

C.8.8 Sample size. The sample size estimate of n=350 patients, 140 per each of the IBET and standard PT arms and 70 in the WL arm, is based on H2, the non-inferiority hypothesis, as this is the most conservative ^{80,94,95}, and on a randomization of 2:2:1 ⁹⁶. In our proposed analysis, this involves testing the IBET*4month and PT*4month interactions in our model. Sample size calculations are based on this comparison and use methods appropriate for ANCOVA analyses, which are equivalent in terms of efficiency to our linear model as noted above. in randomized trials 87. For the non-inferiority test the method is based on performing a one-sided twosample t-test sample size calculation at the alpha=0.025 level for the between group difference at the 4 month time point, multiplied by a factor 1-(rho)^2, where rho represents the Pearson correlation between baseline and follow-up time point outcome measures ⁹⁷. This sample size is then adjusted to compensate for potential missing observations due to attrition. Based on data from our other OA studies, we assume a correlation of 0.6 between WOMAC scores at baseline and at 4 months and an SD for WOMAC scores of 17.5. With 80% power, alpha=0.025, SD=17.5, rho=0.60, and a 10% attrition rate by 4 months, 140 patients in each of the IBET and standard PT groups, need to be enrolled at baseline to identify less than a 5 point difference in mean WOMAC scores between the two treatment groups. We selected the 10% attrition rate based our prior research of behavioral interventions for OA of similar duration ⁵⁴. For H1, with alpha=0.05, SD= 17.5, rho=.6, and approximately 10% attrition rate by 4 months, we have 80% power to detect moderate effect size of 0.35, corresponding to a 6.1 point difference (approximately 13% improvement, which corresponds to a clinically relevant difference) in mean total WOMAC scores at 4 months for either of the 2 intervention compared to WL

control. For the remaining secondary outcomes we will also be powered to detect a moderate 0.35 effect size difference for either of the two intervention compared to the WL control group. We did not conduct a power analysis for the HTE analysis for Aim #3 because we are proposing a descriptive HTE ⁸⁹ and have followed the PCORI Methods Report on this issue. However, our analyses for Aim #3 will provide meaningful and practical data to Stakeholders and organizations with potential to incorporate the IBET program – for example, whether patients with different characteristics differentially benefit from IBET vs. standard PT for knee OA.

C.9.0 Data Management and Quality Control. Study tracking data will be entered into a database created by expert programmers at the UNC Sheps Center for Health Services Research, which has been developed and refined over many years in the context of other clinical trials. This database includes safeguards for ensuring tracking data are collected reliably for all participants (e.g., required fields, limited sets of appropriate responses) and will be thoroughly tested by the study team prior to beginning the clinical trial. This database can be easily customized for the proposed project. We are also able to randomize participants within this database. Customized reports allow the research assistant and project coordinator to identify daily tasks in need of completion, as well as generate flow charts to monitor overall study progress. Screening and outcome measures will be recorded in this same database. As with the tracking database, screening and outcome measures will be programmed to ensure reliable data (e.g., required fields, set ranges of responses) and will be thoroughly tested by the study team before beginning the study. The study team will conduct regular checks and cleaning of screening and outcomes data, throughout the study period, to monitor data quality. The database will also house information on study PT visits, including the initial evaluation form and progress notes for all visits.

C.10.0 Project Timeline and Management Plan. We are proposing a 3-year study. The first 4 months will be devoted to start-up activities, including additional stakeholder input on the IBET program and incorporation of modifications accordingly. This phase will also involve training of personnel and finalization of study databases. Enrollment will take place over the next 16 months (through year 2, month 8), with 4-month follow-up completed by year 3 month 1 and 12-month follow-up completed by year 3, month 9. The final 3 months of the project will be devoted to final analyses and dissemination and implementation related activities. This timeline will require us to enroll 21-22 participants per month, and this is very reasonable based on our experience with prior clinical trials and the resources requested for this project (particularly research assistant effort).

C.11.0. Participant Retention.

We will utilize strategies to promote participant retention that have been successful in our prior and ongoing clinical trials of patients with symptomatic OA (which include diverse groups of patients in terms of gender, health status, education level, and race / ethnicity)⁵⁴⁻⁵⁶. First, we have chosen a wait list control group, versus a usual care control group that receives no treatment. We have found that this helps with fostering retention in any study group that is "inactive" at the beginning of the trial period. Second, we are providing compensation that will be adequate to support participants' time and travel for study assessments. Third, we will be working with at least three different PT clinics to deliver that intervention arm; this will minimize driving distances for participants. Fourth, we will make any reasonable accommodation possible for participants to complete their baseline and follow-up assessments. We are selecting assessment sites with convenient parking and at central locations, and we will conduct assessments outside of normal business hours when needed. Although we plan for study assessments to occur in-person, if participants are unable to come to a study location for a follow-up assessment point (but are otherwise eligible to continue the study), we will allow telephone-based assessment in order to minimize loss-to-follow-up. Our main outcome measures (WOMAC) has been validated for telephone administration.

D. Demonstrate the patient-centeredness of the application (Criterion 4)

The proposed project is highly relevant to patients because knee OA is a leading cause of pain and disability ^{98,99}, outcomes of great importance to patients ¹⁰⁰⁻¹⁰². OA-related pain also has a detrimental impact on other important patient-centered outcomes such as depression, anxiety, employment, relationships, sleep, fatigue, employment, and quality of life ^{12,18,103,104}. In addition, arthritis (including knee OA) is a key barrier to engaging in other healthy behaviors, such as physical activity, and it is strongly associated with obesity ¹⁰⁵⁻¹⁰⁷. Therefore interventions that help patients manage knee OA-related pain also have tremendous potential for

affecting other health outcomes of importance to patients. This project addresses two key PCOR questions:

- 1. "What can I do to improve the outcomes that are most important to me?" Specifically, information generated from this project will enable patients with knee OA to know whether participating in an internet-based exercise program may be as effective of an option as standard PT for improving physical activity and associated patient-centered outcomes. Since some patients experience barriers to access to PT for knee OA (e.g., insurance or related, availability of physical therapists, schedule constraints), it is important for patients to know whether there are alternative resources that will help them to improve outcomes like pain and function via support of an appropriate physical activity program.
- 2. "Given my personal characteristics, conditions and preferences, what should I expect will happen to me?" Results of this project (Specific Aim #3) will help patients and providers understand whether patient characteristics (particularly age and baseline physical function) are associated with differential effectiveness of IBET vs. standard PT among patients with knee OA.

REFERENCES CITED

- **3.** Allen KD. Racial and ethnic disparities in osteoarthritis phenotypes. *Curr. Opin. Rheumatol.* 2010;22(5):528-532.

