Objective Physical Function. We will objectively assess physical function using seven tests. This group of tests is relevant to the proposed study because they assess aspects of daily function that require lower extremity strength, and that are often impacted by knee or hip OA. This battery examines balance (4 tests including a side by side stand, semi-tandem stand, tandem stand, and a unilateral stand), time to rise from a chair and return to the seated position for 30 seconds, timed up and go-rising from a seated position, walking a short distance and returning to seated position, and a 2 minute step test. For each test, the possible range of scores is 0-4, for a total range of 0-20.

Depressive Symptoms – Patient Health Questionnaire-8. We have chosen to include depressive symptoms as a secondary outcome because of the close association of these symptoms with pain. Depressive symptoms

and severity will be assessed using the PHQ-8, a reliable and valid measure of depression⁷¹. The PHQ-8 is an eight-item survey derived from the Primary Care Evaluation of Mental Disorders (PRIME-MD) diagnostic tool, and consists of items corresponding to the depression criteria listed in the *Diagnostic and Statistics Manual Fourth Edition* (DSM-IV). Each of the eight questions is scored as 0 (not at all) to 3 (nearly every day), so that total scores range from 0 to 24.

The Knee injury and Osteoarthritis Outcome Score (KOOS). The KOOS is a patient-reported outcome measurement instrument, developed to assess the patient's opinion about their knee and associated problems. The KOOS evaluates both short-term and long-term consequences of knee injury and also consequences of primary osteoarthritis (OA) }. It holds 42 items in five separately scored subscales: KOOS Pain, KOOS Symptoms, Function in daily living (KOOS ADL), Function in Sport and Recreation (KOOS Sport/Rec), and knee-related Quality of Life (KOOS QOL). Some of these items overlap with those with the WOMAC, and in those instances questions will only be asked once.

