C.8.4. Specific Aim #1. H1 (Superiority): Patients who receive either IBET or standard PT will have clinically relevant improvements in pain, stiffness, and function, measured by the WOMAC at 4-month follow up, compared with patients in the WL control group; H2 (Non-Inferiority): The IBET intervention will be non-inferior to the standard PT intervention at 4-month follow-up, indicated by a mean WOMAC score less than 5 points higher than standard PT. For Specific Aim #1, we will use a linear mixed model (LMM) that accounts for the correlation between a participant's repeated measurements over time. Because of the small number of time points, we will apply an unstructured covariance matrix to take into account the within-patient correlation between repeated measures. The fixed-effect portion of the model will have the form: $Y_{it} = \beta_0 + \beta_1 4$ month+ β₂IBET*4month+ β₃PT*4month, where Y_{it} is the WOMAC score for subject i at t=0 and 4 months. We will estimate the parameters in the model and set up contrasts for tests of hypotheses using the SAS procedure MIXED (Cary, NC). Specifically, for H1, we will test for a difference in mean WOMAC scores between the IBET and/or PT group and the WL group at the primary time point of 4 months by testing that β_2 =0 and/or β_3 =0. For H2, we chose a non-inferiority limit of 5 points for mean WOMAC scores because it is reasonable and on the border of what would be considered a clinically important effect ⁸⁶. The null hypothesis in the non-inferiority framework is that IBET is inferior to standard PT in management of OA symptoms. We will test the noninferiority hypothesis by examining the estimate of the contrast β_2 - β_3 . Specifically, we will examine the 95% CI of the estimated contrast β_2 - β_3 , and if the upper limit of the interval is less than the threshold value of 5 points, we will conclude non-inferiority of IBET to PT 81. If we conclude non-inferiority, we test will for superiority of IBET to PT at 4 months by examining the 95% CI of the estimate of β_2 - β_3 for inclusion of 0 and the p-value for the test of the contrast β_2 - β_3 =0. Time is coded in this model to fit a constrained longitudinal data model (cLDA), in which baseline WOMAC score is modeled as a dependent variable in conjunction with the constraint of a common baseline mean across the treatment arms ⁸⁷. In this way, the cLDA model is comparable to an ANCOVA model; the two models are equivalent when there is no missing data. However, unlike an ANCOVA, participants who are missing follow-up measurements are included in the cLDA model because baseline is part of the response vector. For improvement in precision, the model will also be adjusted for enrollment site (stratification variable) 88. Similar procedures will be used to assess all continuous secondary outcomes. C.8.5. Specific Aim #2: H1 (Superiority): Patients who receive either IBET or standard PT will have clinically relevant improvements in pain, stiffness, and function, measured by the Western Ontario and McMasters Universities Osteoarthritis Index (WOMAC) at 12-month follow up, compared with patients in the WL control group; H2 (Non-Inferiority): The IBET intervention will be non-inferior to the standard PT intervention at 12month follow-up, indicated by a mean WOMAC score less than 5 points higher than standard PT. As

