C.8.6. Specific Aim #3: Examine whether individual patient characteristics (particularly age and baseline functional status) are associated with differential improvement in the IBET and / or standard PT interventions. Patients may vary in their response to the intervention programs; this variation is known as heterogeneity of treatment effects (HTE). We will be conducting a descriptive HTE analyses 89. We have two a priori defined patient characteristics (noted above) and will conduct a separate descriptive HTE for each characteristic for primary and secondary outcomes, as defined in the PCORI Methods Report. We will initially treat age as a continuous variable and evaluate whether treatment response varies with increasing age; we will also evaluate treatment response within discrete age categories (e.g., by decade). With respect to functional status, we will evaluate potential differential response on the basis of participants' baseline scores on the SPPT (objective physical function test), since this is a separate measure from our primary outcome (WOMAC). We will initially treat baseline SPPT composite scores as a continuous variable (0-12). We will also evaluate treatment response within discrete baseline SPPT score categories of <5, 5-8, and >8, which have been shown to predict adverse outcomes. We will construct individual and mean trajectory plots of the longitudinal outcome variables by patient characteristics and treatment arm to understand their general trends over the study period. Our general steps in this secondary analysis will be to add the patient characteristics main effect, as well as the interaction variables, to the linear mixed model defined above. We will examine the parameter and 95% CI of the parameter estimates for the 3-way interactions treatment*time*patient characteristic (e.g. IBET*4month*age) to determine whether there is evidence of HTE for that characteristic. New state-of-the art modeling methods have taken the exploration of HTE to the next level, making it possible to explore and identify multidimensional subgroups exhibiting heterogeneous treatment effects. We will explore whether the a priori defined patient characteristics define multidimensional subgroups that exhibit HTE. We will utilize two different analytic strategies for doing so: multivariable logistic regression^{90,91} and recursive partitioning ^{92,93}. Each has unique strengths as well as limitations, and each approaches the problem of identifying the multidimensional subgroups differently. Our general steps in this secondary analysis will be: construction of outcome variables; identification of multidimensional subgroups via logistic regression and recursive partioning; and, finally, examination of treatment effects within the multidimensional subgroups.

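### The chair-rise count, up-and-go time and 2-minute step count enter the plan only as 0-4 scores; analysing the recorded values as well would avoid a loss of information at almost no cost

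*Combined protocol and SAP*

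**What the plan says.** Section C.7.2 (Objective Physical Function) announces the battery: "We will objectively assess physical function using seven tests". It lists four balance stands, a chair-rise test, a timed up and go, and a 2-minute step test. The chair rise is described as "time to rise from a chair and return to the seated position for 30 seconds". The only variable the section defines from these tests is a score: "For each test, the possible range of scores is 0-4, for a total range of 0-20". No cut-points are given.

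Section C.8.4 sets out the constrained longitudinal model for WOMAC and adds: "Similar procedures will be used to assess all continuous secondary outcomes". It does not say whether the function tests enter as scores or as recorded values.

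Section C.8.8 says of the secondary outcomes: "we will also be powered to detect a moderate 0.35 effect size difference" for either intervention against wait list.

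Section C.8.6 (Aim 3) uses the composite with a different range: "We will initially treat baseline SPPT composite scores as a continuous variable (0-12", with categories below 5, 5 to 8, and above 8.

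No section says whether the counts and times are stored, or that they will or will not be analysed.

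**The concern.** A 30-second chair rise and a 2-minute step test naturally give a count, and an up-and-go gives a time. Cutting such a value into five levels has three effects:

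- changes within a level disappear;
- the correlation between baseline and follow-up, from which the model gains precision, becomes weaker;
- a patient who starts at the top score cannot be seen to improve.

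The battery matters more than its secondary status suggests. Under C.4.0 participants are told their assignment, and under C.7.0 only the assessor is blinded. The other patient outcomes are self-reported. The battery is the only performance-based outcome, because the website log-ins and PT visits also listed in C.7.2 record use of the intervention, not function. It is therefore the natural check on whether a self-reported benefit over wait list reflects better function. A real gain becomes a smaller standardised effect once the values are cut.

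**Working it through.** **1. The plan's own power figure.** Inputs from C.8.8: 140 per active arm, 70 on wait list, 10% attrition, correlation 0.6, effect 0.35 SD; the 0.05 alpha is taken as two-sided.

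- Completers: 140 × 0.9 = 126 and 70 × 0.9 = 63.
- Standard error in SD units: √(1 − 0.6²) × √(1/126 + 1/63) = 0.8 × 0.1543 = 0.1234.
- Expected z: 0.35 / 0.1234 = 2.835.
- Power: Φ(2.835 − 1.96) = 80.9%. The stated 80% reproduces.

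**2. What the documents do not supply.** There are no cut-points and no score distributions, so everything below is assumed. The loss can be bracketed but not derived.

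**3. One test, closed form.** Take a normal underlying value with correlation 0.6 between visits, cut at both visits into scores 0 to 4.

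- E = (change in mean score per unit shift)² / variance of the score.
- r = correlation between the baseline and follow-up scores.
- Information retained in the baseline-adjusted analysis: R = E × (1 − 0.6²) / (1 − r²).

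| Assumed shares at scores 0/1/2/3/4 (%) | E | r | R | Loss |
|---|---|---|---|---|
| 10.7/23.65/31.3/23.65/10.7 (near-optimal) | 0.918 | 0.555 | 0.849 | 15% |
| 20 each | 0.888 | 0.548 | 0.812 | 19% |
| 2, then 24.5 each | 0.880 | 0.540 | 0.795 | 20-21% |
| 2/8/15/25/50 | 0.781 | 0.519 | 0.684 | 32% |
| 2/3/8/17/70 | 0.609 | 0.473 | 0.502 | 50% |

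Example, second row: 0.888 × 0.64 / (1 − 0.548²) = 0.568 / 0.700 = 0.812.

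Simulation at the 0.35 SD effect with 126 versus 63 completers gives about 14-21% for well-spread scores, 32% with half the patients at the top and 52% with 70% at the top. The last figure differs slightly from the table because the assumed shares below the top differ and the effect is not infinitesimal.

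**4. In terms of power.** If the effect is 0.35 SD in recorded units, power after cutting is Φ(2.835 × √R − 1.96).

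| Loss | R | Power | Sample-size equivalent (1/R) |
|---|---|---|---|
| none | 1.00 | 80.9% | 1.00 |
| 14% | 0.86 | 74.8% | 1.16 |
| 21% | 0.79 | 71.2% | 1.27 |
| 32% | 0.68 | 64.7% | 1.47 |
| 52% | 0.48 | 50.2% | 2.08 |

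**5. The summed score.** A sum averages out some of the coarseness, and the balance components are scored in either case. Assume two scored balance components (five components at 0-4 would match the stated 0-20), correlation between tests of 0.3-0.7, the same cuts and the same shift in every component. Compare this with the same sum using recorded values for the three timed or counted tests. The loss is about 4-7% with well-spread scores and 28-36% with 70% at the top. Against 80.9%, the same formula gives power of 79.3% to 78.1% (R = 0.96 to 0.93) and 67.2% to 62.1% (R = 0.72 to 0.64).

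**6. The range of the total.** Seven tests at 0-4 give 7 × 4 = 28. Counting the four stands as one component gives 4 × 4 = 16. The stated 20 needs five components, and the 12 in C.8.6 needs three. Neither stated total follows from the listed tests.

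**The case against.** The strongest reply is that any headline percentage describes an assumed scoring, not this plan's. That stands. The large losses need half or more of the patients at the top score on each test, and nothing in the documents supports that; eligible patients are symptomatic and not meeting activity guidelines. With well-spread scores the loss for the sum is only a few percent.

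It is also fair that cutting before analysis is inferred. C.7.2 defines only scores, which makes that the natural reading, but no passage excludes analysing the recorded values. The calculations further assume normal data and a uniform shift, with no patients unable to do a test. An ordinal score may deal with inability more simply.

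Three stronger readings are tempting and are not supported:

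- A reader might infer that the power statement in C.8.8 is wrong. It is in SD units of whatever variable is analysed, and it reproduces.
- A reader might infer that coarse scores make IBET look falsely non-inferior to PT. Non-inferiority is defined on WOMAC with a 5-point margin, and no margin exists for function.
- A reader might infer that the summed score should give way to an average of the three recorded values. With evenly spread scores and two balance components responding equally, the scored sum keeps about 96-108% of the information in such an average. Replacing it is therefore not a clear gain, and it would drop balance, a stated domain.

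What survives is the loss for each test, which appears under every set of cuts tried.

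**Conclusion.** The point holds as a cheap improvement to a secondary outcome; it is not an error that undermines the trial. The plan defines the chair rise, up-and-go and step test only through 0-4 scores and a total, and it names no analysis of the recorded counts or times.

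The cost to any one test is about 14-21% of its information if scores spread well, and up to about 52% if 70% of patients start at the top. For a five-component sum it is about 4-7% up to 28-36%. These ranges rest on assumed cut-points, score distributions, correlations between tests and number of balance components. They should not be quoted as a property of this trial. The direction is firm; the size is not.

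The mismatch among seven tests at 0-4, a total of 0-20 and a composite of 0-12 is a separate defect. It can be read directly from the text and needs no assumption.

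**What to change.** In C.7.2, state that the chair-rise count, the up-and-go time and the 2-minute step count are stored as recorded. In C.8.4, name each as a secondary outcome analysed in recorded units with the same constrained longitudinal model, transforming time if it is skewed. Pre-specify how patients unable to do a test are handled.

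Keep the summed score, including balance, as a reported composite. Separately, give its components and cut-points so that its range can be checked, and reconcile it with the 0-12 range and the categories in C.8.6 before using it for Aim 3. Those categories are stated for a 0-12 composite and cannot be carried over unchanged to a 0-20 score.

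The cost is three more secondary results to report and one rule for inability. A count or time has to be observed before it can be scored, so keeping it should need at most a database field, although the documents do not confirm that it is kept.

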C.8.1 General Overview. Our statistical approach is guided by the PCORI Methods Report. For the superiority hypotheses (H1, H3), analyses will be conducted on an intent-to-treat (ITT) basis; patients will be analyzed in the arm to which they were randomized, regardless of adherence, using all data up to the 12-month follow-up or last available measurement prior to exclusion or dropout ⁷⁹. Additional exploratory analyses focusing on alternative, more restrictive analytic cohorts (e.g., as treated) may be considered for the superiority hypotheses, to provide additional information about the impact of magnitude of exposure to the interventions. For non-inferiority hypotheses (H2, H4), the ITT analysis would not be the conservative approach; therefore, it is recommended to perform analysis on both an intent-to-treat and per-protocol basis ^{80,81}.

C.8.2 Descriptive statistics. Descriptive statistics, including graphical displays, will be used to summarize all

study variables overall and by randomization arm. We will construct individual and mean trajectory plots of the

longitudinal outcome variables to understand their general trends over the study period. In addition, we will explore the variability and correlation structure of the longitudinal outcome variables. All statistical analyses will be performed using the SAS (Cary, NC) software package / R (www.r-project.org).

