C.8.3 Missing Data. Because the main predictors of interest, intervention arm and patient characteristics, are collected at baseline, we do not anticipate much missing data in these variables. There may be missing values in the outcome measures due to dropout, death, a missed interim assessment, or item non-response. Given a thorough understanding of the missing data mechanism, it is possible to use all of the available information in analysis, rather than using only subjects with completely observed information. Our main analysis technique for the primary outcomes, general linear mixed models via maximum likelihood estimation, implicitly accommodates missingness when it is due either to treatment, to prior outcome, or to other baseline covariates included in the model, defined as missing at random 82. Therefore, inferences will be valid even if we have differential dropout by intervention arm. If the missing values are related to other measured patient factors, such as age or comorbidity, then multiple imputation (MI) provides a framework for incorporating information from these variables, while still preserving a parsimonious main treatment effect model 83, and is described as a significant advantage in recommendations from Panel on Handling Missing Data in Clinical Trials 84. Depending on the type and scope of missing data, MI will be conducted via the SAS procedure PROC MI or the SAS macro IVEware (http://www.isr.umich.edu/src/smp/ive/). If the probability of dropout is related to the actual missing response (which is unobserved because it is missing) or to other unobserved quantities, the missing data due to dropout is considered missing not at random (MNAR) or nonignorable 85. There is a possibility that data may be MNAR, and we propose as additional sensitivity analyses to explore MNAR methods, including selection and pattern-mixture models 85.

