
described above, will use a linear mixed model (LMM), adding in the 3 parameters for the 12-month period (12month, IBET*12month, PT*12month). We will follow the same testing procedures for the 12-month parameters as described for the 4-month. Similar procedures will be used to assess longer term effects of all continuous secondary outcomes at 12-months.

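### The Aim 1 model stops at month 4, so a patient who misses month 4 but attends month 12 adds only a baseline score to the primary contrast; one model on months 0, 4 and 12 would serve both aims

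*Combined protocol and SAP*

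**What the plan says.** - **C.8.4 (Aim 1).** The response "is the WOMAC score for subject i at t=0 and 4 months". The fixed effects are a common baseline mean, a 4-month term and the two arm-by-4-month terms, with unstructured covariance. The primary superiority tests (β2, β3) and the non-inferiority contrast (β2 − β3, margin 5 points) come from this fit.
- **C.8.5 (Aim 2).** The same type of model is used, "adding in the 3 parameters for the 12-month period". On testing it says: "We will follow the same testing procedures for the 12-month parameters as described for the 4-month".
- **C.8.1.** The superiority hypotheses are analysed by intention to treat, "using all data up to the 12-month follow-up or last available measurement prior to exclusion or dropout". Non-inferiority gets both an intention-to-treat and a per-protocol analysis.
- **C.8.3.** Outcome data may be missing because of "dropout, death, a missed interim assessment, or item non-response". The section favours using all available information over complete cases.
- **C.1.0.** There are three measurement times: baseline, 4 months and 12 months. Month 4, the primary time point, is therefore the only interim assessment.

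**The concern.** The missing-data pattern that C.8.3 anticipates, a missed interim visit, can occur only at the primary time point. For such a patient the 12-month WOMAC carries information about the unobserved 4-month value, and the Aim 1 model leaves it out although it will be in the database at analysis. The Aim 2 fit does use it, and it re-estimates the 4-month terms along the way. When some patients miss month 4 and return, the two fits can give slightly different values for the same 4-month contrast. That would matter only if the upper confidence limit fell close to the 5-point margin, but in that case it should be clear beforehand which fit counts.

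C.8.6 adds interaction terms, including 4-month ones, to the mixed model defined earlier without saying which of the two fits is meant.

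**Working it through.** **Inputs from the plan (C.8.8):** SD 17.5, baseline-to-4-month correlation 0.60, margin 5, one-sided alpha 0.025, 80% power, 10% attrition by month 4, arms of 140/140/70.

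**Assumed, because the plan gives no value:** 4-to-12-month correlation r(4,12) of 0.6 to 0.8; baseline-to-12-month correlation r(0,12) of 0.6, with 0.55 as a check; share f of month-4 missers who return at month 12, from 0 to 100%. Patients seen at month 4 are taken as also seen at month 12.

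**1. The plan's own figure.** 2 × (1.96 + 0.8416)² × 17.5² / 5² gives 193 per arm. Multiplying by 1 − 0.6² = 0.64 gives 123.5, so 124. Dividing by 0.90 gives 138, against 140 stated; this reproduces. With 126 evaluable per arm, SE(β2 − β3) = 17.5 × √0.64 × √(2/126) = 1.764, and power = Φ(5/1.764 − 1.96) = 0.809. For superiority (126 against 63, 6.1 points), power is 0.806, against 0.80 stated.

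**2. What month 12 adds.** Per arm, n = 126 patients are seen at month 4 and m = 14f miss it but return. After adjustment for baseline, the variance of the 4-month contrast is multiplied by

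1 − ρ² × m/(n + m), where ρ = [r(4,12) − 0.6 × r(0,12)] / √[(1 − 0.6²)(1 − r(0,12)²)].

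The SD of the difference between the two estimates is 1.764 × √[ρ² × m/(n + m)]. Example with r(4,12) = 0.8, r(0,12) = 0.6, f = 100%: ρ = 0.44/0.64 = 0.6875, ρ² = 0.4727, m/(n + m) = 14/140 = 0.1, factor 0.953.

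| r(4,12) | f | Variance factor | SE | Power | SD of difference (points) | Equivalent extra patients per arm |
|---|---|---|---|---|---|---|
| any | 0% | 1 | 1.764 | 0.809 | 0 | 0 |
| 0.6 | 20% | 0.997 | 1.761 | 0.810 | 0.098 | 0.4 |
| 0.6 | 100% | 0.986 | 1.751 | 0.815 | 0.209 | 1.8 |
| 0.7 | 50% | 0.985 | 1.751 | 0.815 | 0.215 | 1.9 |
| 0.7 | 100% | 0.972 | 1.739 | 0.820 | 0.296 | 3.7 |
| 0.8 | 50% | 0.975 | 1.742 | 0.819 | 0.278 | 3.2 |
| 0.8 | 100% | 0.953 | 1.722 | 0.827 | 0.383 | 6.3 |

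With r(0,12) = 0.55, the factor runs from 0.996 (f = 20%, r(4,12) = 0.6) to 0.960 (f = 80%, r(4,12) = 0.8).

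**3. Do the two fits differ?** Both models were fitted by maximum likelihood to 150 simulated trials (true IBET minus PT difference 0, r(4,12) = 0.7, r(0,12) = 0.6, 10% missing month 4). With complete data and with monotone dropout, the two 4-month contrasts were identical. With half of the missers returning, the difference had SD 0.215 and maximum 0.59 points; with all returning, SD 0.295 and maximum 0.84. The mean difference was −0.01 and 0.01, so no systematic shift. With the same SE of 1.764 applied to both fits, the non-inferiority conclusion changed in 4% and 5.3% of these trials.

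**4. Assumptions about missingness.** Two deliberately one-sided illustrations in the IBET arm only, with r(0,12) = 0.55 and r(4,12) = 0.7. The mean of a standard half-normal is 0.798.

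- *Selective return.* Month 4 is missing at random in 10%. The half with a 12-month score better than the mean return; the rest do not. Shift of the three-point contrast ≈ −(0.37/0.6975) × (0.05/0.95) × 0.6975 × 17.5 × 0.798 = −0.27 points, towards non-inferiority. The two-point contrast is unbiased.
- *Month-4 missingness tied to the 12-month score.* 15% miss month 4 if their 12-month score is worse than the mean, and 5% if better. Shift of the two-point contrast ≈ [(0.425 − 0.475)/0.90] × 0.37 × 17.5 × 0.798 = −0.29 points. If all of them are seen at month 12, the three-point fit allows for this.

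Here 0.37 = 0.70 − 0.60 × 0.55 and 0.6975 = 1 − 0.55².

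**The case against.** The strongest reply is that a baseline and 4-month model is a legitimate analysis of a 4-month endpoint. It matches the ANCOVA basis of the sample size, and it keeps every randomised patient with a baseline score. C.11.0 allows telephone follow-up, which should make missed month-4 visits fewer. C.8.3 also provides conditional multiple imputation and sensitivity analyses for data missing not at random. The 10% in C.8.8 is attrition, and if none of those patients return the gain is exactly zero. All of this stands, and it is why the point is minor.

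Four stronger readings are tempting, and the documents do not support them:

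- *The plan sets up two rival primary results.* C.8.4 ties the 4-month tests to the Aim 1 fit, and C.8.5 tests only 12-month parameters. The second 4-month estimate is a by-product.
- *The two fits will always disagree.* They coincide unless patients miss month 4 and return.
- *C.8.4 flatly contradicts C.8.1.* The all-data sentence is written for the superiority hypotheses, and as a general overview it could be met by Aims 1 and 2 together. The fit between the sections is poor, but they are not irreconcilable.
- *The three-point model needs a strictly weaker assumption.* It lets month-4 missingness depend on an observed 12-month score, but it also needs month-12 missingness to be ignorable. Step 4 shows that either model can be the biased one.

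**Conclusion.** The point holds as a minor improvement. As written, 12-month scores from patients who missed month 4 do not inform the primary contrast, although the plan foresees such patients and states an all-data principle for superiority. Using those scores would cut the variance of the IBET minus PT contrast by 0 to about 5%. Power would move from 0.809 to at most about 0.83, and that top value needs every month-4 misser to return and a 4-to-12-month correlation of 0.8. The two fits would typically differ by 0.1 to 0.4 points (one SD) when there are returners, against an SE of 1.76 and a margin of 5.

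These sizes rest on an assumed return rate and assumed correlations with month 12. The stated sample size is sound and needs no change. Nothing here suggests that the planned two-point analysis is invalid.

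**What to change.** In C.8.4 and C.8.5, pre-specify one constrained longitudinal model with t = 0, 4 and 12 months, unstructured covariance and adjustment for enrollment site, fitted to all randomised patients. Take the primary 4-month contrasts and the 12-month contrasts from that single fit. Use the same model form for the per-protocol non-inferiority analysis, and name it as the base model for C.8.6. Align the data statement in C.8.1 with it.

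State that the model also relies on month-12 missingness being ignorable, and keep the months 0 and 4 fit as a sensitivity analysis. If the sponsor prefers to keep the two-point model as primary, the minimum is a sentence saying that the 4-month contrast is reported from that fit only, with C.8.1 reworded to match.

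The cost is wording in the analysis plan. The 0/4/12 model is already planned for Aim 2, no extra data are needed, and C.10.0 already places the final analyses after 12-month follow-up.
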